PROTOCOL OF A NON-INTERVENTIONAL CLINICAL STUDY

Protocol title: An observational, open-label, multi-center prospective study for assessing the patients' adherence to TRAVATAN® in routine daily clinical practice.

Study code: TRAVO

Protocol no: CRO-Sponsor-Travo

Date: 28 Aug 2015

Version: 1

Authors: [name]
Consultant in Ophthalmology Department, 401 General Military Hospital of Athens

Contract Research Organization CRO
(CRO):

Sponsor: SPONSOR

This confidential document is the property of the sponsor. No unpublished information contained in this document may be disclosed without prior written approval of the sponsor.

STATEMENT OF COMPLIANCE

This document is a clinical research protocol. The study will be conducted in compliance with the protocol and in accordance with the International Conference on Harmonisation (ICH) guidelines for Good Clinical Practice (GCP), with the ethical principles laid down in

the Declaration of Helsinki and with the Greek National Organization of Medicines (EOF) regulations.

All personnel involved in the conduct of this study have completed human subjects' protection training.

Study Protocol Synopsis

Title:	An observational, open-label, multi-center prospective study for assessing the patients' adherence to TRAVATAN® in routine daily clinical practice.
Phase:	Phase IV
Number of study sites:	40
Primary Objective:	To investigate patients' adherence to TRAVATAN® (Travoprost 40µg/ml Eye Drops) in adult patients with ocular hypertension or ocular hypertension or open angle glaucoma, when administered according to standard clinical practice.
Secondary Objective:	To identify potential factors that may be associated with TRAVATAN® non-adherence in daily clinical practice.
Study Design:	Multicenter, prospective, non-interventional, one arm, open label cohort study of patients with ocular hypertension or open angle glaucoma receiving TRAVATAN®. The total duration of the study is 36 weeks (12 weeks recruitment period and 24 weeks follow-up period).
Target population:	Male and female patients with ocular hypertension or open angle glaucoma, aged ≥ 18 years, receiving Travoprost 40µg/ml Eye Drops.
Inclusion criteria:	
 • Adult patient (≥ 18 years old) with ocular hypertension or open angle glaucoma • Patient receiving TRAVATAN®. • Patients willing and able to provide written informed consent

	
personally or by legal proxy.
 
 • Patients willing to comply with all study procedures and to be available for the duration of the study.
Exclusion criteria:	
 • Patient with uncontrolled IOP\geq21 mmHg. • Pregnant or nursing (lactating) women, where pregnancy is defined as the state of a female after conception and until the termination of gestation, confirmed by a positive hCG laboratory test • Patients in treatment for ocular diseases (including OH or OAG) with more than one therapy. • Patient with hypersensitivity to the active substance or to any of the excipients of this medicinal product. • Current enrollment in other clinical trial.
Data collection plan	At baseline, at 8 weeks and end of follow-up period (24 weeks).
Primary endpoint:	Proportion of patients reporting high adherence to TRAVATAN® at 24 weeks defined as a Morisky Medication Adherence Scale (MMAS-4) score equal to 0.
Secondary endpoints:	
 • Proportion of patients with a Medication Persistence Ratio (MPR), defined as the number of days without receiving medication after study enrolment divided by the number of days participating in the study, less than 0.20. • Proportion of patients encountering difficulties with medication supply due to coexisting medical conditions. • Proportion of patients encountering difficulties with medication supply due to lack of insurance coverage. • Proportion of patients encountering difficulties with medication

	
supply due to inability to access or difficulty accessing pharmacy.
 
 • Proportion of patients with TRAVATAN® discontinuation during the follow-up period.
Sample size:	
The sample size calculation was conducted with the precision-based sample size calculation.
 
In order to calculate a 95% confidence interval for the proportion of patients reporting high adherence to TRAVATAN® at 24 weeks, which is expected to be 80% with a margin error (Δ) (Okeke et al, 2009) no more than 2%, the required sample size is at least 1537 patients. A total sample size of at least 1843 patients (20% additional) will allow compensation for incomplete datasets.

Statistical methods:	
Demographic and clinical/prognostic data of the patients at baseline will be described with numerical and graphical summary statistics. The statistical significance of the proportion of patients reporting high adherence to TRAVATAN® will be assessed using a binomial test and the respective 95% confidence interval (CI). For the secondary endpoints, categorical data will be analyzed using a binomial test with the respective 95% CI, and continuous data will be analyzed using the paired t-test or the Wilcoxon signed rank test, depending on the nature of the data. The association between categorical variables will be tested using a chi-squared test and/or logistic regression. A result will be considered significant when $P \leq 0.05$. The statistical analysis will be performed using SPSS v.21

STUDY CONTACT DETAILS

Principal Investigator:

CRO:

Sponsor:

PROTOCOL SPONSOR APPROVAL

An observational, open-label, multi-center prospective study for assessing the patients' adherence to TRAVATAN® in routine daily clinical practice Study code: TRAVO

Signature:

SPONSOR

Date:

(DD-mmm-YYYY)

PROTOCOL AUTHORS APPROVAL

Signature:

[name]

Consultant in Ophthalmology Department,401 General Military Hospital of Athens

Date:

(DD-mmm-YYYY)

INVESTIGATOR'S AGREEMENT

I have read the foregoing protocol, entitled "An observational, open-label, multi-center prospective study for assessing the patients' adherence to TRAVATAN® in routine daily clinical practice" and agree to conduct the study as detailed herein and to inform all who assist me in the conduct of this study of their responsibilities and obligations.

Principal Investigator's Name

Signature

Date

Investigational Site

LIST OF ABBREVIATIONS AND KEY TERMS

Abbreviation	Full term
AE	Adverse Event
ADR	Adverse Drug Reaction
CRF	Case Report Form
CRO	Contract Research Organization
GCP	Good Clinical Practice
ICF	Informed Consent Form
ICH	International Conference on Harmonization
SAE	Serious Adverse Event
SmPC	Summary of Product Characteristics
VA	Visual Acuity
VF	Visual Fields
PEX	Pseudoexfoliation
PGs	Prostaglandins
logMAR	Logarithm of the Minimum Angle of Resolution
IOP	Intraocular pressure
BAC	Benzalkonium chloride
OH	Ocular Hypertension
OAG	Open Angle Glaucoma

Table of Contents

1. Background	12
1.1 Introduction	12
1.2 Name and description of study product	15
Study objectives	17
1.3 Primary objective	17
1.4 Secondary objective	17
1.5 Study design	17
2. Study population	18

1.1 Introduction

Data from population-based surveys (PBS) indicate that glaucoma is the leading cause of irreversible blindness; however, when detected and treated early, blindness is usually preventable (Quigly. 1996. Br J Ophthalmol). Accounting for 8% of blindness among the 39 million people who are blind world-wide in 2006 (Pascolini et Mariotti. 2012 Br J Ophthalmol), the number of individuals estimated to be bilaterally blind due to glaucoma was projected to increase from 8.4 million in 2010 to 11.1 million by 2020 (Quigley et Broman. 2006 Br J Ophthalmol). Open angle glaucoma (OAG) is a multifactorial characteristic optic neuropathy characterized by progressive retinal ganglion cell death and corresponding characteristic visual field loss (Siesky et Harris. 2012 Adv Ther) traditionally classified, concerning the cause, as primary and secondary.

Primary open angle glaucoma (POAG) is characterized by the absence of any anatomic identifiable underlying predisposing cause of events that led to aqueous outflow obstruction and raised IOP, whereas increased resistance in outflow system associated with other ocular or systemic disorders such as exfoliated material, pigment dispersion, inflammation or tumor cells and IOP increase, is classified as secondary open angle glaucoma (American Academy of Ophthalmology, The eye M.D. Association, 2012, Glaucoma, Section 10, 250p).

Another variant of primary open angle is low-tension or normal-tension glaucoma, which is characterized by patients without elevated intraocular pressure, who may develop optic nerve head degeneration that results in a loss of peripheral vision. Additionally, it is estimated that a large population has elevated intraocular pressure without glaucomatous damage on standard clinical examination (Leibowitz et al. 1980 Surv Ophthalmol). Nevertheless, given that a substantial percentage of the optic nerve fibers are lost before glaucomatous visual field defects can be recognized, there is a need for early detection and treatment (Kerrigan-

Baumrind et al. 2000 Invest Ophthalmol Vis Sci.). Individuals who have elevated intraocular pressure without detectable optic nerve damage are at increased risk for developing POAG and are sometimes referred to as “ocular hypertensives” or “glaucoma suspects” (Quigley et al. 1994 Arch Ophthalmol). Although the etiology of glaucoma is multi-factorial, intraocular pressure (IOP) is the only modifiable factor in glaucoma management that has been proven to alter the natural course of the disease (Friedman et al. 2004. Am. J. Ophthalmol.). Open angle glaucoma is the most prevalent form in Caucasian and African population (Gordon et al. 2002 Arch Ophthalmol). The Ocular Hypertension Treatment study confirmed that age, cup-disc ratio, corneal thickness and baseline intraocular pressure are predictive factors for the development of POAG in individuals (Sommer et al. 1991 Arch Ophthalmol), whereas low diastolic perfusion pressure seems to be another factor leading to POAG (Tielsch et al. 1995. Arch Ophthalmol). Certain conditions, including refractive errors, diabetes mellitus, cardiovascular disease and retinal vein occlusion, have been associated with glaucoma (Wong et Klein. 2003 Ophthalmology).

Regarding low – tension glaucoma, it is a condition, which is characteristically bilateral and progressive, often despite lowering IOP. The Collaborative Normal-Tension Glaucoma Study (CNTGS) found that lowering IOP reduced the rate of visual field progression, confirming that IOP has a clear role in this disease (Coll Normal-Tension Glau Study Group. 1998 Am J Ophthalmol).

Secondary open-angle glaucomas mostly encountered are pseudoexfoliation (PEX) and pigmentary. In PEX, an age-related, complex, generalized disorder of the extracellular matrix, the progressive accumulation of intraocular abnormal fibrillar materials in the anterior segment is considered the primary cause of chronic IOP elevation (Schlotzer-Schrehardt et Naumann,. 2006, Am J Ophthalmol). Pigmentary OAG typically develops in young myopic patients with pigment dispersion syndrome, which is characterized by melanin pigment liberation from the iris pigment epithelium (Sugar. 1966 Am J Ophthalmol).

Despite significant surgical and laser parasurgical progress, lowering IOP with topical drugs remains the initial and probably main treatment for most patients, including those with normal-tension glaucoma or ocular hypertension (Russo et al. 2008 Clin Ophthalmol). The eye drops work by enhancing the drainage of fluid from the eye or by reducing the production of aqueous fluid in the eye. These medications will usually have to be administered for the rest of the patient's life, and regular use according to a physician's instructions is absolutely necessary to control the disease. If eye drops and/or oral medications are not effective in controlling the intraocular pressure, there are several laser or surgical procedures that might be employed, which have shown to halt or significantly slow the progression of the disease (Gedde et al. 2007 Am J Ophthalmol).

While safe and effective treatments for glaucoma exist, their effectiveness is compromised by poor compliance. Patients who have problems with their topical glaucoma medication are acknowledged to be at higher risk for poor compliance, frequent medication switching, and surgery. Patient satisfaction with therapy and its associated benefits have until recently taken second place to efficacy. Lemij et al conducted a transverse cross-sectional epidemiological survey among glaucoma patients receiving therapy with prostaglandin analogs. The primary objective was to determine and characterize patient satisfaction with glaucoma therapy, and the secondary objective was to identify factors that may contribute to poor patient satisfaction. Ophthalmologists in the Netherlands included 199 patients and 164 were analyzed (Lemij et al, 2015, Clin Ophthalmol). Patients were predominantly elderly with early, primary, open angle glaucoma. Eighty-nine percent of them stated they were satisfied or very satisfied with their treatment. However, signs of ocular surface disorder on ophthalmological examination were evident in 44% of patients, corneal fluorescein staining was positive in 28% of patients, and 38% of patients were using tear substitutes. The prevalence of blepharitis/meibomian gland dysfunction and dry eye was more than twice as high after the commencement of therapy compared with before therapy. Univariate analysis revealed that patient dissatisfaction with their glaucoma therapy was statistically significantly

($P < 0.001$) associated with the presence of ocular surface disease, hyperemia, ocular signs, symptoms upon and between instillation, and the use of tear substitutes. Apparently, patients in the present study are satisfied with their treatment; 89% expressed satisfaction compared with only 11% who professed dissatisfaction. The results suggest that even if local adverse events and ocular surface disease, in particular, contribute to glaucoma patient dissatisfaction, only a minority of patients expressed such dissatisfaction. At the time of the study, most (94%) of the patients included were receiving preserved preparations. Further studies should evaluate the influence of preservative on patient satisfaction.

Recent reports indicate that more than 90% of patients with glaucoma fail to refill their ocular medications continuously during the first year of therapy and that less than 60% continue to refill eye drop prescriptions at 1 year (Friedman et al, 2007, *Inv Ophth Vis Sci*; Nordstrom et al, 2005, *Am J Ophth*). It has been suggested that medication adherence may be improved substantially by choosing a drug that needs to be taken less often (Norell, 1981, *Am J Ophthalmol*).

1.2 Name and description of study product

TRAVATAN® 40µg/ml eye drops have been registered for therapeutic use since 2001 (Whitson, 2002 *Expert Opin Pharmacother*). The current preparation of TRAVATAN® 40µg/ml contains 40 mcg of travoprost, a prostaglandin F2a analogue, in 1 ml solution. The preparation of TRAVATAN® 40µg/ml also contains 10 micrograms of polyquaternium-1 (POLYQUAD), 7.5 mg of propylene glycol, and 2 mg of polyoxyethylene hydrogenated castor oil 40 (HCO-40) in 1 ml solution. Further excipients are mannitol, sodium chloride, sodium hydroxide and/or hydrochloric acid disodium, boric acid, and purified water (SPC Travatan, 2013). Travoprost is a member of the prostaglandin analogue class of intraocular pressure-lowering drugs that also include other substances such as latanoprost or bimatoprost. Like other prostaglandin analogues, travoprost lowers intraocular pressure by enhancing the

egress of aqueous humor through both the uveoscleral and trabecular outflow pathway (Lim et al. 2008 Ophthalmology). Travoprost acts by binding to a specific receptor for prostaglandin (FP receptors/highly concentrated in the longitudinal ciliary muscle, iris, sphincter muscle and retina), and increases the flow of aqueous humor out of the eye, thereby reducing the pressure within the eye and the risk of nerve damage and blindness. In detail, travoprost is an isopropylester pro-drug that is hydrolyzed by corneal esterases into its biologically active free-acid form which is a highly selective, potent antagonist for the FP prostanoid receptor. Once travoprost acid binds to prostaglandin FP receptors, a numerous physiologic responses within ciliary muscle cells result in the remodeling of the extracellular matrix by creating spaces between the ciliary muscle fiber bundles. Thus, travoprost acid increases outflow primarily by the uveoscleral pathway. Reduction of IOP starts approximately two hours after administration and the maximum effect is reached after 12 hours. Travoprost has been compared to b-blockers such as timolol, other prostaglandin analogues such as latanoprost and bimatoprost. Summarizing the data comparing travoprost with other drugs, similar IOP reductions were seen with travoprost, bimatoprost or latanoprost (Denis et al. 2007 Clin Ophthalmol) whereas travoprost monotherapy lowers IOP by 6.5-9 mmHg and it is statistically superior or equal to timolol 0.5% dosed twice daily (Parrish et al. 2003 Am J Ophthalmol).

The need for sterilization in multi-dose eye drops requires the inclusion of an antimicrobial less toxic preservative in these solutions, such as polyquad (polyquaternium), which is a family of polycationic polymers. At least 37 different polymers exist, under the polyquaternium designation, but polyquaternium -1 is commonly used as multipurpose solution for contact lens care and has shown a good tolerability and safety profile compared to other multipurpose solutions (Lipener. 2009. Adv Ther). Polyquad is a cationic polymer of many quaternary ammonium structures with a 27-fold higher molecular weight than BAC, which lacks an hydrophobic region and as a result has no surfactant properties. Due to these

two chemical properties, Polyquad is unable to penetrate mammalian cells and cause cytotoxic effects (Tripathi et al. 1992 Eye Toxic Res). Except for concentrations of 0.5% or above, polyquad did not cause significant changes on the ocular surface compared with saline, whereas BAC induced apparent toxic effects at 0.1% and 0.5% concentrations, with a dramatically and extremely rapid destruction of ocular cells (Labbé et al. 2006 J Ocul Pharmacol Ther). Although Polyquad is considered relatively safe, it has been noted that this preservative dose have potent toxicity on the barrier function and cell viability after long-term exposure (Nakagawa et al. 2012 Invest Ophthalmol Vis Sci).

Study objectives

1.3 Primary objective

The primary objective of the current study is to investigate patients' adherence to TRAVATAN® (Travoprost) in adult patients with ocular hypertension or open angle glaucoma, when administered according to standard clinical practice.

1.4 Secondary objective

The secondary objective comprises the following: To identify potential factors that may be associated with TRAVATAN® non-adherence in daily clinical practice.

1.5 Study design

Multicenter, open – label, one – arm, prospective, non-interventional cohort study of patients with ocular hypertension or open angle glaucoma receiving TRAVATAN®. The total duration of the study is 36 weeks (12 weeks recruitment period and 24 weeks follow-up period). The recruitment period may be extended until the total number of patients is reached.

2. Study population

2.1 Target population

The target population of the current clinical study is male and female patients with ocular hypertension or open angle glaucoma, aged ≥ 18 years, receiving Travoprost, according to standard clinical practice.

2.2 Inclusion criteria

To be eligible to participate in this study, a patient must meet all the following eligibility criteria at baseline:

- Adult patient (≥ 18 years old) with ocular hypertension or open angle glaucoma
- Patient receiving TRAVATAN®.
- Patients willing and able to provide written informed consent personally or by legal proxy.
- Patients willing to comply with all study procedures and to be available for the duration of the study

2.3 Exclusion criteria

A patient will be excluded from the study if any of the following exclusion criteria apply:

- Current enrolment in other clinical trial.
- Patient with uncontrolled IOP ≥ 21 mmHg.
- Pregnant or nursing (lactating) women, where pregnancy is defined as the state of a female after conception and until the termination of gestation, confirmed by a positive hCG laboratory test
- Patients in treatment for ocular diseases (including OH or OAG) with more than one therapy.

- Patient with hypersensitivity to the active substance or to any of the excipients of this medicinal product.

3. Study endpoints

3.1 Primary endpoints

The primary endpoints of the study is the Proportion of patients reporting high adherence to TRAVATAN® at 24 weeks defined as a Morisky Medication Adherence Scale (MMAS-4) score equal to 0.

3.2 Secondary endpoints

The secondary endpoints of the study comprise the following:

- Proportion of patients with a Medication Persistence Ratio (MPR), defined as the number of days without receiving medication after study enrolment divided by the number of days participating in the study less than 0.20.
- Proportion of patients encountering difficulties with medication supply due to coexisting medical conditions.
- Proportion of patients encountering difficulties with medication supply due to lack of insurance coverage.
- Proportion of patients encountering difficulties with medication supply due to inability to access or difficulty accessing pharmacy.
- Proportion of patients with TRAVATAN® discontinuation during the follow-up period.

4. Total study duration

Total study duration is three (3) months recruitment period and 6 months follow-up period for each patient.

5. Data collection plan and study variables

Data pertinent to the present study will be collected on three visits and recorded on the Case Report Form (CRF). A schedule of patients' visits and assessments are presented in attached Table.

5.1 Baseline visit (week 0)

The Baseline visit will include the screening phase during which inclusion and exclusion criteria are checked, the patient is informed about the study, and informed consent form is signed. Should the patient is eligible for participation in the study and upon signature of the informed consent form; the following data will be recorded: demographic data, medical history (type of glaucoma, date of diagnosis, previous and current treatment for glaucoma and duration of administration), IOP measurement, comorbidities and concomitant medications.

5.2 Visit at week 8

During the visit at week 8, the following will take place: administration of the MMAS-4 questionnaire, calculation of the Medication Persistence Ratio and the following data will be recorded: description of potential factors associated with non-adherence, treatment discontinuations and adverse events.

5.3 Final visit (week 24)

During the final visit, the following will take place: administration of the MMAS-4 questionnaire, calculation of the Medication Persistence Ratio and the following data will be recorded: description of potential factors associated with non-adherence, treatment discontinuations and adverse events.

5.4 MMAS-4

The Morisky Medication Adherence Scale (MMAS) is a generic self-reported, medication-taking behavior scale, validated for hypertension but used for a wide variety of medical conditions. The original version of the scale (MMAS-4) consists of four items with a scoring scheme of “Yes” = 0 and “No” = 1. The items are summed to give a range of scores from low adherence (3-4) to high adherence (0) (Morisky et al, 1986, Med Care).

5.5 MPR

The Medication Persistence Ratio (MPR) was defined as the number of days without receiving medication after study enrolment divided by the number of days participating in the study. High adherence was defined as a value less than 0.20.

6. Treatment and concomitant medication

Since this is an observational, non-interventional study, the treatment schedule is defined according to investigator’s criteria. Treatment with TRAVATAN® should be according to the indication for treatment as defined in the Summary of Product characteristics (SmPC) and according to standard clinical practice. During this non interventional study, any changes and/or additions to the concomitant medications are allowed according to investigator’s criteria. All concomitant medications will be recorded on the CRF.

7. Treatment discontinuation

A patient should be withdrawn from the study if:

- according to the investigator’s criteria treatment with TRAVATAN® should be discontinued
- the patient withdraws her consent for participation in the study
- any of the exclusion criteria becomes applicable.

The reason of patient’s withdrawal should be recorded on the CRF.

8. Safety assessments

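### For patients withdrawn because TRAVATAN is discontinued, the MPR stops counting at withdrawal, so an early stop with few missed days can be classed as high adherence

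*Protocol*

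**What the plan says.** In Section 5.5 of the protocol the ratio is "defined as the number of days without receiving medication after study enrolment divided by the number of days participating in the study". The section adds: "High adherence was defined as a value less than 0.20". Section 3.2 makes the proportion of patients below that cut-off the first-listed secondary endpoint, with the same denominator ("divided by the number of days participating in the study less than 0.20"). The synopsis repeats it.

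Section 7, on treatment discontinuation, begins "A patient should be withdrawn from the study if" and lists three triggers. The first is the investigator's judgement that "treatment with TRAVATAN® should be discontinued". The others are withdrawn consent and an exclusion criterion that comes to apply. The patient therefore leaves the study, not only the treatment.

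Follow-up is 24 weeks (Section 1.5: "12 weeks recruitment period and 24 weeks follow-up period"). Sections 5.2 and 5.3 and the flow chart schedule "calculation of the Medication Persistence Ratio" at week 8 and week 24 only, and no withdrawal visit is described. Section 3.2 lists "Proportion of patients with TRAVATAN® discontinuation during the follow-up period" as a separate endpoint and does not link it to the MPR classification.

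**The concern.** A persistence ratio should get worse when a patient comes off the drug. Under Sections 5.5 and 7 read together, it cannot do so for a patient whom the investigator takes off TRAVATAN: the denominator ends at withdrawal, and the untreated days that follow are never counted. The cut-off of 0.20 is then applied to windows of very different length, for example 28 days for one patient and 168 for another.

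At stake is the meaning of the first secondary endpoint. The same patient can be counted as discontinued in one endpoint and as highly adherent in another. Two patients with identical time on drug can also receive opposite labels, depending only on whether they were formally withdrawn.

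**Working it through.** The protocol states no MPR-based figure, so there is none to reproduce. The check applies its own definition.

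Inputs:
- Planned follow-up: 24 × 7 = 168 days (Section 1.5). Week 8 is day 56.
- Cut-off for high adherence: below 0.20 (Section 5.5).
- Stop day *s* and missed days *m* before the stop: not in the protocol, assumed here for illustration.

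Formulas:
- Withdrawn at the stop, as written: MPR = *m* / *s*.
- Stops but stays in the study to week 24, as written: MPR = (*m* + 168 − *s*) / 168. A fixed 168-day window gives a withdrawn patient this same value.

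| Stop day | Missed days | Withdrawn, as written | Stays in study, or fixed window |
|---|---|---|---|
| 28 | 0 | 0/28 = 0.000 | 140/168 = 0.833 |
| 28 | 3 | 3/28 = 0.107 | 143/168 = 0.851 |
| 56 | 6 | 6/56 = 0.107 | 118/168 = 0.702 |
| 84 | 10 | 10/84 = 0.119 | 94/168 = 0.560 |
| 112 | 11 | 11/112 = 0.098 | 67/168 = 0.399 |

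Every value in the third column passes and every value in the fourth fails.

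Minimum time on drug. Over 168 days a patient with no missed days passes only if 168 − *s* is below 0.20 × 168 = 33.6. Day 134 gives 34/168 = 0.202 (fails) and day 135 gives 33/168 = 0.196 (passes). For a withdrawn patient, the definition as written sets no minimum.

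Visit schedule. A patient withdrawn on day 28 has no scheduled MPR. One withdrawn on day 84 has a scheduled value only at week 8. Even if all 10 missed days fell before that visit, it is 10/56 = 0.179, still below 0.20. Whether the value is frozen, kept from week 8 or missing, the stop is not registered.

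Effect on the proportion (illustration only). Suppose a share *q* of patients is withdrawn off drug before day 135, and 80% of the rest are high. Over a fixed window the endpoint is 0.80(1 − *q*). If all withdrawn patients are scored and pass, it reads 0.80(1 − *q*) + *q*. If 80% of them pass, or if they are left out as missing, it reads 80%.

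| *q* | Fixed window | All withdrawn pass | 80% pass, or left out |
|---|---|---|---|
| 5% | 76% | 81% | 80% |
| 10% | 72% | 82% | 80% |
| 20% | 64% | 84% | 80% |

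The gap is 4 to 5, 8 to 10 or 16 to 20 percentage points. It would vanish if missing values were counted as failures and no withdrawn patient were scored, but the protocol does not say so.

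**The case against.** The strongest reply is that the problem is narrower than it looks.

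- **Who is affected.** A reader might infer that the clock stops for anyone who stops the drops. Section 7 does not say that. A patient who stops unprompted is not automatically withdrawn, keeps accruing untreated days, and fails after an early stop. This objection stands and limits the point to formally withdrawn patients. It also exposes the opposite classification of equal time on drug.
- **Best score for early stoppers.** A reader might infer this too, but a completer with no missed days also scores 0, and a patient withdrawn with 20% or more of days missed still fails. Withdrawal removes the penalty for stopping; it does not confer a bonus.
- **Schedule.** With MPR due only at weeks 8 and 24, some withdrawn patients may never be scored. That is correct, and handling of missing values may sit in a statistical analysis plan that is not shown. But the denominator is fixed by the protocol, so a plan that counted days after discontinuation would be changing a stated definition.
- **An on-treatment ratio is legitimate.** Reported beside the discontinuation proportion, it is a defensible pair, and a physician's decision to stop is not patient behaviour. This has force, but such a measure should not be called persistence, and the separate endpoint does not correct the MPR label.

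**Conclusion.** The point holds for patients withdrawn when the investigator discontinues TRAVATAN. For them the MPR cannot register the stop, and a patient withdrawn early with few missed days can be classed as highly adherent (0.12 against 0.56 in the day-84 example). This follows from the stated definition and the withdrawal rule together; it is not a matter of absent detail.

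The individual examples rest only on assumed stop days and missed days. The effect on the reported proportion is unknown, because the protocol gives no discontinuation rate; the percentages above are illustrations.

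Two further inferences are not supported. A reader might conclude that the primary endpoint is inflated by the same withdrawals, but MMAS-4 at week 24 does not use this denominator, and any bias there would depend on how missing scores are handled. A reader might also want the discontinuation proportion replaced by a time-to-event estimate. That choice is commonly left to the analysis plan, and the size of any bias would rest on assumed rates of stopping and loss.

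**What to change.** Define the week-24 MPR over the planned 168 days from enrolment, or to the actual week-24 visit. Count each day after TRAVATAN discontinuation as a day without medication. Treat the MPR as missing when follow-up is lost for reasons unrelated to stopping, rather than computing it on the short window. If an on-treatment ratio is also wanted, label it as adherence while on treatment and report it beside the discontinuation proportion.

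The cost is one definition and a stop date. Sections 5.2 and 5.3 already record discontinuations but do not name the date, so the CRF should capture it. No treatment or withdrawal decision changes. The downsides are a lower MPR success rate, that stops decided by the physician count as non-persistence, and an assumption that TRAVATAN is not restarted after withdrawal, when the patient is no longer observed.
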